## **Study Protocol**

We were able to show the target engagement in the R21 phase of this study. The major goal of the R33 phase is to prepare for a future randomized controlled clinical trial (RCT) by piloting a feasibility study that includes an active control arm and multimodal pre- and post-treatment measures. We aimed to achieve the following: (1) test the feasibility of recruiting, randomizing and retaining patients for VR social skills training; 2) compare the social skills training VR compared an active control VR game by measuring behavioral and neural changes after VR intervention.

## **R33 PROJECT DESIGN**

This is a small pilot study to compare the outcome measures after the VR social skills training compared with an active control video game. Participants with schizophrenia (SZ) undergo training. Participants with schizophrenia are randomly assigned to the social skills VR condition or the active control condition at baseline. After completing all the baseline assessments including clinical symptoms ratings, social cognitive assessments, and resting state fMRI scan, participants are asked to visit the lab for 8 sessions (twice a week) to complete the VR training or the active control condition. After 8 sessions, there is a post-training assessment that includes symptoms ratings, social cognitive assessments and resting state fMRI scan. Then participants cross over to the other condition for 8 sessions, after which there is a final post-training assessment. Demographically matched control participants are recruited to obtain comparison data but they do not undergo any training. Research staff conducting clinical symptoms and social functions assessments are blind to the VR training or control condition assignment.

VR Condition: The same procedure as outlined in R21 phase with the determined optimal dose of 8 sessions administered over 4-5 weeks.

Active Control Condition: We control for the number of lab visits, duration of game playing and computer use in the active control group by administering a commercially available video games which do not require any simulated social interactions but instead, support cognition.

## Participants:

This proposal involves testing individuals with schizophrenia (SZ), and healthy control subjects (CO). All subjects are recruited from Nashville area. The following general inclusion/exclusion criteria apply to all subjects: (1) no diagnosed organic brain disease, brain lesions, history of head traumas, hormonal disorders, neurological disorders or other conditions that involve the degeneration of the central nervous system (e.g. multiple sclerosis), (2) no substance/alcohol abuse/dependence during the past 1 year, (3) no tardive dyskinesia, (4) WASI IQ> 85. Low IQ makes it less likely that the participants understand the instructions and comply and thus, might introduce confounding factors. Since we need to establish the initial feasibility and acceptability, it is essential that they understand the training instructions. Therefore, we only included those participants with IQ > 85 and those who are able to travel to

the lab independently. Any co-existing medical conditions (e.g., diabetes), smoking habits, and medications were noted. Diagnostic interviews (SCID) were conducted for Axis I for all subjects.

Inclusion/exclusion criteria for schizophrenia group: Participants were recruited from outpatient day facilities in Nashville. DSM-5 criteria were used to diagnose SZ. Those with a history of head injury, substance abuse, neurological diseases (e.g., stroke, tumors), hormonal disorders (e.g. Cushing's disease) or IQ<85 will be excluded. All patients were taking antipsychotic medications. When someone is very psychotic, any social remediation training is not going to be effective. Recruiting outpatients who are stabilized on medication, allowed us to work with the population whose psychotic symptoms are partially in remission but are still experiencing significant social cognitive impairments. The range of symptoms scores of our outpatient sample in the past 14 years in Nashville is very comparable to the scores reported by other groups. The mean SAPS score of our SZ outpatients from the past 14 years was 15.34 (S.D.= 8.36) and the mean SANS was 23.71 (S.D.=14.73). These scores are almost identical to the published mean SAPS (16.8, s.d.=14.2) and SANS (23.0, s.d.=14.6) scores from the FBIRN consortium 143. For this R33 study, if the SAPS or SANS score is 1 s.d. above the mean of our typical outpatient sample (i.e. SAPS > 23; SANS > 38), we planned to place that patient on a wait list until his/her symptom scores fall within 1 s.d. of the mean. This additional precaution should be able to address potential concerns that psychotic individuals may be adversely affected by virtual reality video games. (See below). One note of concern is the potential adverse effects of the COVID pandemic. This study was on hold for 2 years during the pandemic because we were unable to open the lab to test and train participants due to the concerns of infection. After the study was able to start in 2021, we noted worsening of physical health of the SZ individuals who had consented to participate prior to the pandemic.

Inclusion/exclusion criteria for the healthy control group: Healthy participants were recruited from the Vanderbilt University web-based recruitment panel and from Nashville Metro area via signs placed in public buildings (e.g. supermarkets, Laundromats, gyms, cafes). Exclusion criteria were: Axis I psychotic disorders in themselves or their families (e.g. schizophrenia, bipolar disorder), history of head injury, substance abuse, neurological diseases (e.g., stroke, tumors), hormonal disorders (e.g. Cushing's disease) and IQ<85.

Additional screening for neuroimaging in R33: There are further exclusion criteria for fMRI in the R33 phase because those at primary risk from exposure to high-intensity magnetic fields must be excluded. Exclusion criteria are implanted medical devices (e.g. pacemakers, cochlear implants, IUDs), implanted paramagnetic prostheses, and augmentations (e.g. steel pin). People at secondary risk are also excluded (e.g. asthma, heart disease, diabetes etc). Potential participants must fill out the standard questionnaire used with all patients undergoing MRI at the Vanderbilt University Medical Center. If a potential participant meets the criteria for inclusion in the fMRI component, he/she will go through the informed consent procedure for neuroimaging. If a participant does not meet the inclusion criteria for fMRI part, he/she will not participate in the neuroimaging but will participate in all other parts provided that he/she meets the inclusion/exclusion criteria described above.

Age range: Included age range was 18 and 65. In our actual recruited sample the youngest participant was 20. Aging increases the likelihood of introducing confounding factors such as cognitive decline, dementia, hormonal changes and others. This age group will be

familiar with video games and computers. This is important because the VR training and active control training are similar to video games.

**Ethnic composition and diversity**: Nashville metropolitan area is increasingly ethnically diverse. We tried to recruit ethnically representative samples of SZ and CO. In our past studies in Nashville, about 20% of our participants were African-Americans.

Gender: We aimed to recruit 50% women.

Procedure: All participants undergo baseline assessments at T1, including fMRI. The research staff conducting assessments are blind to the treatment groups and those who supervise the training session do not do assessments. SZ play the VR game or active control game in the lab. The VR dosing was determined in the R21 phase (8 sessions). After the completion of the training, they are given the post-training assessments and then switch over to the other condition for 8 sessions. We use the same dose for the active control condition. The VR and control game performance scores are saved at each session. To boost adherence, we text 1 day before and 2 hours before the visit. Subjects are paid per session and receive a small bonus at the end of the training. An exit interview is conducted to find out about acceptability and engagement.

Measures: At baseline (T1), we assess social cognitive functions, symptoms and conduct a resting state fMRI scan. To elucidate the mechanism of change, we focus on the social attention and the integrity of the social brain network that supports social cognition. Training begins within a week of completing the assessments. Within a week of the completion of the training, we conduct post-treatment assessments. Next, SZ participants cross over to the other condition and complete 8 sessions, after which they undergo another post-training assessments. Control participants complete only the baseline assessments.

Data Analysis Behavioral Measures: The same general framework as those described for the R21 phase were used. We use univariate and multivariate mixed effects models (LMMs) to assess the effects of the VR intervention relative to the control game condition on the social assessment and symptom measures and other measures noted above (see below for fMRI). We assess effects both at post-Intervention for the VR condition and compare them with the post-intervention after the active control condition. As described in the R21 phase, we will also conduct intensive analyses within the VR condition of the trajectory of performance across 8 sessions of the social skills training. Using structural equation modelling approaches that are appropriate for the moderate sample size, we will further conduct mediational analyses assessing the important question of whether changes in social attention and in the trajectory of performance during training mediate the effects of treatment on social functioning and symptoms. As in the R21 phase, we will also compare post-treatment SZ to normative distributions, and model drop-out and attrition.

Neuroimaging data: VR task provides extensive opportunities to exercise social attention and simulation. We will examine the activity of the pSTS, IPL, and IFG in relation to social attention and social functioning. Our past work indicates that action imitation and simulation deficits in SZ but repeated practice improve performance. Furthermore, a recent study showed

that simulation work exercises in VR significantly improved work function in real life. We will examine resting state functional connectivity data in relation to the primary outcome measures. Data Acquisition: A Philips Intera Achieva 3T scanner is used to collect high-resolution T1 anatomical images (170 slices; 1x1x1 mm), and T2\*-weighted functional images parallel to the AC-PC line (gradient-echo T2\*-weighted EPI; 25 slices; TR=2000ms; TE=35ms, flip angle=79°; FOV=240x240mm^2; voxel size =1.875x1.875x5mm^3). FMRI data analysis: BrainVoyager QX1.1 is used. Anatomical volumes are transformed into a common stereotactic space, and functional volumes for each subject are aligned to the transformed anatomical volumes. Standard pre-processing is performed: temporal high-pass temporal frequency filtering, linear de-trending, 3D motion correction, slice scan time correction, and spatial smoothing with a 6mm Gaussian kernel (full width half-maximum). Individual subject analyses are performed using a GLM with the 6 experimental conditions entered as regressors, and data are collapsed across runs. First, we compare SZ vs. CO at baseline to determine the integrity of the social brain network (group-by-instruction-by-stimulus type mixed-effects analysis) at resting state. Statistical maps are created for each group separately and for the group comparison. Multiple comparisons are corrected at p=.05 by Monte Carlo simulations to arrive at a cluster threshold. We will compare the pre- and post-treatment cortical activity patterns for each treatment regimen. We will also assess the relation between changes in activation of the social brain network and in social attention on the behavioral task and whether such changes predict changes on social outcome measures.

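### The post-VR versus post-control contrast states no periods, baseline or carryover assumption; read over both crossover periods, it is shifted by half of (control carryover minus VR carryover)

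*Combined protocol and SAP*

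**What the plan says.** All references are to the combined protocol and SAP.

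- **R33 Project Design.** "Participants with schizophrenia are randomly assigned to the social skills VR condition or the active control condition at baseline". They are assessed after 8 sessions. "Then participants cross over to the other condition for 8 sessions, after which there is a final post-training assessment". The Procedure and Measures paragraphs repeat this sequence. Post-training assessments fall no later than a week after training ends, and no washout before the second condition is stated. The documents label only the baseline (T1); T2 and T3 below mean the first and second post-training assessments.
- **Data Analysis Behavioral Measures.** Mixed effects models are planned for VR relative to the control game, and "We assess effects both at post-Intervention for the VR condition and compare them with the post-intervention after the active control condition". The paragraph names no period, sequence or carryover term and no first-period comparison. It refers to a framework from the R21 phase that is not in the documents.
- **Study Protocol.** The first aim is to "test the feasibility of recruiting, randomizing and retaining patients for VR social skills training"; the second is to "compare the social skills training VR compared an active control VR game by measuring behavioral and neural changes after VR intervention". The phase is meant to prepare for a later randomised trial.
- **Active Control Condition.** The control uses "commercially available video games which do not require any simulated social interactions but instead, support cognition".

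**The concern.** Each participant who completes the study gives one post-VR and one post-control score, from different periods. The natural reading of the contrast is therefore a comparison over both periods, although the text does not say so outright. The intervention is skills training, and nothing in the documents says that its gain is gone when the second condition is assessed. On the two-period reading, half of the post-control scores may still contain some VR gain, and half of the post-VR scores some control gain.

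The VR-control comparison is the second stated aim. If the contrast, its baseline and the carryover assumption are left open, the same data can understate or overstate the VR effect, and a reader of the result cannot tell which.

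**Working it through.** **Inputs.** The design and contrast come from the sections above. The documents give no effect size, SD, sample size, allocation ratio or persistence for this comparison, so there is no figure to reproduce and every number below is an assumption. Let v and c be the VR and control effects, Lv and Lc the shares of each that persist to the next assessment, and p1, p2, p3 the period means at T1, T2 and T3.

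**Cell means.**
- VR first: T2 = p2 + v; T3 = p3 + c + Lv·v
- Control first: T2 = p2 + c; T3 = p3 + v + Lc·c

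**Post-score reading (post-VR minus post-control).**
- VR first: v - c - Lv·v + (p2 - p3)
- Control first: v - c + Lc·c + (p3 - p2)
- Mean of the two: v - c + (Lc·c - Lv·v)/2

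The period means cancel with equal sequences, or are absorbed by a period term. The carryover part remains in either case. With Lv = Lc = L the result is (1 - L/2)(v - c), which is attenuation when v > c. With c = 0 it is (1 - L/2)v.

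The direction depends on the inputs. With v = 1.2, c = 0.6 (true difference 0.6) and Lv = 0.25:
- Lc = 0.75: 0.6 + (0.45 - 0.30)/2 = 0.675, or +12.5%
- Lc = 1: 0.6 + (0.60 - 0.30)/2 = 0.75, or +25%

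If the sequences are unequal and no period term is fitted, with a share f VR-first and c = 0, the estimate is v(1 - fL) + (1 - 2f)(p3 - p2). At L = 0.5 and no drift this is 0.80v at f = 0.4 and 0.70v at f = 0.6.

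**Change-score reading (change from each period's own start).**
- VR first: v - (c + Lv·v - v) = 2v - c - Lv·v
- Control first: (v + Lc·c - c) - c = v - 2c + Lc·c
- Mean: 1.5(v - c) + (Lc·c - Lv·v)/2

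Period means again cancel in the average. At equal L this is (3 - L)/2 × (v - c). In general it is unbiased only when Lv·v - Lc·c = v - c.

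**T2 by randomised sequence.** (p2 + v) - (p2 + c) = v - c, whatever the carryover.

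**Simulation.** 20,000 trials per setting, 15 per sequence, correlation 0.5, true difference 0.6 SD, equal L, no dropout. Each cell shows mean; RMSE; 95% CI coverage.

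| L | Post-score | Change-score | T2 adjusted for T1 |
|---|---|---|---|
| 0 | 0.60; 0.18; 95% | 0.90; 0.44; 85% | 0.60; 0.32; 95% |
| 0.25 | 0.53; 0.20; 93% | 0.83; 0.39; 89% | 0.60; 0.32; 95% |
| 0.5 | 0.45; 0.24; 87% | 0.75; 0.35; 93% | 0.60; 0.32; 95% |
| 1 | 0.30; 0.35; 64% | 0.60; 0.32; 95% | 0.60; 0.32; 95% |

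Separate large-sample mixed models (4,000 subjects, true effect 1) gave 1.03, 0.75 and 0.48 at carryover differences (VR minus control) of 0, 0.5 and 1. The results were the same with or without a period term or T1.

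**Precision (SD units, n per sequence, correlation r).**
- Pooled post-score SE = sqrt((1 - r)/n) = sqrt(0.5/15) = 0.183
- T2 SE = sqrt(2(1 - r²)/n) = sqrt(1.5/15) = 0.316
- Ratio = sqrt(2(1 + r)) = 1.73, 1.84 and 1.90 at r = 0.5, 0.7 and 0.8

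**Gap between the T2 and pooled estimates (same setting).** The mean gap is 0.60 - 0.45 = 0.15 at L = 0.5 and 0.60 - 0.30 = 0.30 at L = 1, against an SD of about 0.26. In simulation it exceeded 1.96 SD in only 9% and 20% of trials, and had the wrong sign in 29% and 13%.

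**The case against.** The strongest reply is that the documents show an under-specified contrast, not a bias. They never say that the contrast spans both periods. Even if it does, carryover that is nil or equal in amount leaves the post-score estimate unbiased. The R21 framework might supply model terms. Feasibility is the first aim, and the design section describes the study this way: "This is a small pilot study to compare the outcome measures after the VR social skills training compared with an active control video game". The T2 comparison is also noisy. In the setting above its power is about 43%, against 89%, 66% and 35% for the pooled estimate at L = 0, 0.5 and 1, and the pooled estimate has the smaller RMSE until L is about 0.86.

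Most of this stands. It limits the severity and makes T2 a supportive estimate, not a replacement. It does not remove the need to state the contrast and its assumption, because the supplied text does neither.

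Four stronger inferences are tempting but unsupported:

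- **That the plan will understate the VR effect.** Downward bias under equal shares needs v > c. The documents give neither effect and neither persistence. That the control games support cognition leaves control carryover open, but does not show that more control gain than VR gain persists.
- **That change scores should be avoided.** They are unbiased at L = 1, where post scores lose half the difference, and their coverage is already better at L = 0.5 (93% v 87%). Neither choice is safe without a carryover assumption. Moreover, only the word for change in the second aim suggests this reading for behavioural outcomes. The explicit pre-post wording is in the neuroimaging section, which this point does not cover.
- **That comparing T2 with the pooled estimate reveals carryover.** At pilot size the gap is mostly noise.
- **That the later trial will be wrongly sized.** The documents give no rule for sizing it from this estimate.

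**Conclusion.** The point holds in conditional form. If the behavioural contrast spans both periods, with equal sequences or a period term, it equals the true VR-control difference plus half of (control carryover minus VR carryover), and a period term does not correct this. Where VR has the larger effect and the same share L of both gains persists, the attenuation is L/2: 12.5%, 25% and 50% at assumed L of 0.25, 0.5 and 1. More control than VR carryover reverses the direction. Under the change-score reading with equal L, the estimate is 1.50, 1.38, 1.25 and 1.00 times the true difference at L = 0, 0.25, 0.5 and 1.

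Actual size and direction are unknown, and the unseen R21 framework may already cover part of this. Severity is minor to should-fix: the comparison is the second aim of a small pilot that lists feasibility first, but the remedy is cheap and uses data already scheduled.

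**What to change.** For behavioural and symptom outcomes:

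1. State the contrast, the baseline it uses, and that it spans both periods, if that is intended.
2. Fit condition and period terms, and state the assumption under which the estimate is unbiased. For post scores this is nil carryover, or carryover equal in amount for the two conditions. For change from each period's own start it is full persistence or, in general, VR carryover minus control carryover equal to the true difference.
3. Report beside it, as a supportive estimate with its confidence interval, the T2 score by randomised sequence adjusted for T1.

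A sequence-by-period term fitted to T2 and T3 alone is no substitute, because it is aliased with condition. If the R21 framework already covers any of these items, quote it in the plan. The Age range paragraph shows that recruitment has taken place, so label the addition post hoc if outcome data have been seen.

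The cost is revised wording and one extra model, with no new patients or visits. The T2 standard error is about 1.7 to 1.9 times the pooled one (assumed correlation 0.5 to 0.8). The plan should therefore say that a gap between the two estimates is not a test for carryover.

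### Training-performance trajectory is named as a mediator of VR versus the control game, but neither reading of the supplied text gives an interpretable indirect effect

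*Combined protocol and SAP*

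**What the plan says.** All references are to the combined protocol and SAP.

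- **Treatment effect.** Under Data Analysis Behavioral Measures, mixed models will "assess the effects of the VR intervention relative to the control game condition on the social assessment and symptom measures".
- **Trajectory.** The same paragraph plans "intensive analyses within the VR condition of the trajectory of performance across 8 sessions of the social skills training". No analysis of a control-game trajectory is described.
- **Mediation.** The next sentence plans structural equation models to ask whether "changes in social attention and in the trajectory of performance during training mediate the effects of treatment on social functioning and symptoms". It does not say which condition's trajectory is meant, and it gives no path model.
- **Data available.** Under Procedure: "The VR and control game performance scores are saved at each session".
- **Control task.** Under Active Control Condition, the comparator is "commercially available video games which do not require any simulated social interactions but instead, support cognition".
- **Timing.** Under R33 Project Design: "After 8 sessions, there is a post-training assessment that includes symptoms ratings, social cognitive assessments and resting state fMRI scan". Participants then cross over. Under Measures: "Within a week of the completion of the training, we conduct post-treatment assessments".
- **Framework.** The behavioral analysis paragraph opens with "The same general framework as those described for the R21 phase were used". The R21 text is not part of the documents.

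**The concern.** Mediation of VR versus control needs two paths: from condition to mediator, and from mediator to outcome given condition. A measure that exists only under VR, or that is a different quantity under each condition, does not supply an interpretable first path.

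The risk is in interpretation. A correlation between learning rate in the VR game and later social outcome could be reported as evidence that skill gained in VR drives the benefit. The same correlation can arise when VR has no benefit, for example if faster learners improve more in any period. The study is meant to prepare for a randomized trial, so a mislabelled mechanism claim could be carried forward.

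**Working it through.** The plan states no sample size, effect size or correlation for this analysis, so there is no figure to reproduce. Step 1 follows from the design. Steps 2 to 4 use assumed values throughout and are not forecasts for this trial.

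**1. VR trajectory only.** With VR data alone, the condition indicator equals 1 for every record. The matrix [intercept, condition] has two identical columns, so its rank is 1 of 2. The condition-to-mediator path *a*, and hence the indirect effect *a × b*, cannot be estimated. Only the slope-outcome association remains.

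**2. How such an association can arise with no VR effect.** Take a two-period crossover with half the participants VR first. Let T be a stable trait (variance 1) and e independent noise.

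- VR slope: S = l·T + √(1 − l²)·e
- Outcome in each period, identical under VR and control: Y_next = 0.6·Y_prev + 0.8·(g·T + √(1 − g²)·e)

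The VR-minus-control effect is zero. The test is the partial correlation of S with post-VR outcome given pre-VR value and sequence, on N − 4 df. If baseline is independent of T, the partial correlation for those who have VR first is l × g. With l = g = 0.55 that is 0.55 × 0.55 = 0.30. Over both sequences the simulated value is 0.29, and the VR slope predicts the control-period outcome equally well (0.29).

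| l = g | Trait-baseline correlation | Partial r | p < 0.05 at N = 20 to 40 |
|---|---|---|---|
| 0 | 0 | 0 | about 5% |
| 0.30 | 0 | 0.09 | 6.3% to 8.4% |
| 0.55 | 0 | 0.29 | 21.9% to 43.5% |
| 0.55 | 0.5 | about 0.22 | about 14% to 27% |
| 0.55 | 0.8 | about 0.14 | about 9% to 14% |
| 0.70 | 0 | 0.47 | 52.6% to 86.2% |

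The rate depends strongly on the trait correlations and on whether the trait is already reflected in the baseline outcome. The documents fix neither.

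**3. Both games' scores.** Express each slope in session-1 SDs per session, so that units drop out. Fit outcome on condition and slope M, with outcome SD 1.

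- a = mean slope (VR) − mean slope (control)
- b = (r₁s₁ + r₂s₂) / (s₁² + s₂²), where r and s are the slope-outcome correlation and the slope SD in each condition

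Assume a VR mean slope of 0.10, both slope SDs 0.05, and r₁ = 0.30.

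- r₂ = 0.30: b = (0.015 + 0.015) / 0.005 = 6.0. Control mean slopes of 0.05, 0.10 and 0.20 give a = 0.05, 0 and −0.10, so a × b = +0.30, 0 and −0.60 SD.
- r₂ = 0: b = 0.015 / 0.005 = 3.0, and a × b = +0.15, 0 and −0.30 SD.

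Only the control game's learning curve changed, yet the sign reversed. This is a parallel-group sketch with one mediator. It shows the dependence in principle and does not model the crossover.

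**4. Precision of the replacement analysis.** For a partial correlation of 0.30 with two covariates, Fisher z = 0.3095 and SE = 1/√(N − 5).

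- N = 20: SE 0.258, 95% CI −0.19 to 0.67
- N = 30: SE 0.200, 95% CI −0.08 to 0.61
- N = 40: SE 0.169, 95% CI −0.02 to 0.57

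**The case against.** The strongest reply is that the restriction to VR belongs to the preceding sentence. The mediation sentence stands alone and speaks of training in general. The Age range paragraph uses that word for both conditions, and scores from both games are saved. A two-condition model is therefore a fair reading, and the R21 framework may define its metric.

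Much of this stands. A reader might infer that the plan commits itself to a VR-only mediation model, or that trajectory mediation is impossible on any reading. The documents support neither. The two-condition reading still leaves a gap, because the control games are different, non-social tasks and the supplied text has no common metric and no control-trajectory analysis. Saved control scores make a model possible to fit but do not make the indirect effect interpretable.

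It is also fair to say that the false-association rates are driven by free choices. The 22% to 44% case assumes that baseline outcome is unrelated to the trait; relaxing that lowers it considerably, and weak traits give rates close to nominal. The rates should not be read as this trial's error rate.

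Finally, a reader might extend the criticism to social attention. That is not supported. The list of post-training assessments does not name it, but it may fall under social cognitive assessments. The Measures paragraph makes it a mechanism focus, and the fMRI data analysis text refers to change in it on a behavioral task. If it is taken the same way after each condition, it can be contrasted between them. Its limit is different: a mediator measured at the same assessment as the outcome gives no time order between the two.

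**Conclusion.** The point holds as a minor one, with medium confidence. Using the VR trajectory alone, no indirect effect of VR versus control is estimable; this needs no assumed values. Using both games, the indirect effect depends on game scoring and difficulty unless a common metric exists outside the supplied text. On either reading the supplied plan does not support a mediation claim for the performance trajectory.

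The main VR-versus-control comparison is not affected, and nothing here supports a wider criticism of it. What is at stake is one secondary mechanistic claim in a feasibility pilot. With no VR effect and trait correlations of 0.55, the illustrative false-association rate runs from about 9% to 44% at N of 20 to 40, as the assumed trait-baseline correlation goes from 0.8 to 0. With trait correlations of 0.30 it is near 5% to 9%. No single rate can be attached to this trial.

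**What to change.** 1. Limit between-condition mediation to measures taken identically after both conditions, such as change in social attention on the same behavioral task. Confirm that the measure is taken at each post-training assessment, and state that measuring mediator and outcome at the same assessment limits causal interpretation.
2. Analyse each participant's VR performance slope over the 8 sessions within the VR condition, as a predictor of post-VR outcome. Adjust for the pre-VR value (T1 if VR came first, the post-control assessment if VR came second) and for sequence.
3. Suggested wording: *Mediation of VR versus control will be examined only for measures taken identically after both conditions. VR performance slope will be examined within the VR condition, adjusted for pre-VR value and sequence, and reported as exploratory association, not mediation.*
4. If the R21 framework does define a common metric, reproduce it in the SAP with the model and its handling of the crossover, so that the claim can be judged.
5. The Age range paragraph already describes the recruited sample. If data collection is complete, label the change post hoc.

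The cost is SAP wording and one changed model, with no new data. The relabelled regression can still produce the associations shown in step 2 of the working; what changes is the claim made from it. That claim is weaker and, on the intervals in step 4, imprecise.
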